10.2 Secondary study parameter(s)

Intergroup comparison of total time from discontinuation of hypnotic drug delivery until discharge from the post-anaesthesia care unit will be performed by means of an unpaired t-test or a Mann-Whitney-U-test.

Intergroup comparison of the incidence of postoperative delirium will be performed by means of an chi square test.

Posthoc intergroup comparison of hypnotic depth as measured by DSA is performed as follows: DSA patterns recorded during the procedure are categorised and assigned to three conditions of the specific DSA pattern for GA; appropriate DoH (presence of high power delta and alpha oscillations on the power spectrum), to deep DoH (presence of high power delta, alpha and theta oscillations on the power spectrum), to light DoH (presence of high power delta with the absence of high power alpha oscillations and the presence of high power beta oscillations). Intergroup comparison will be performed by a means of a chi-square test.

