1.2 Density spectral array monitoring

Electroencephalographic density spectral array (DSA) is a three dimensional method to display electroencephalogram (EEG) signals consisting of the EEG frequency (y-axis), the power of the EEG signal (colour-coded to be integrated into a two dimensional plot) and the development of the EEG power spectrum over time (x-axis) (see figure 1).⁷

[figure not shown]

Figure 1 density spectral array (DSA)

Density spectral array has been developed to facilitate the interpretation of unprocessed electroencephalogram signals. It has multiple advantages compared to the widely used electroencephalogram-based indices, or processed EEG monitors.

Electroencephalographic density spectral array shows age-dependent changes in EEG effects of general anaesthetics in children. These age-related changes likely reflect ongoing development within the brain.^{5,6,8}

Furthermore, we know that different anaesthetics act at different molecular targets and neural circuits. This results in anaesthetic drug specific EEG signatures that are readily visible in DSA.⁷ The index-based indices, or processed EEG monitors assume the same index value defines the same level of unconsciousness for all anaesthetics.

Because of the limitations of processed EEG monitors, recently published articles emphasize the use of raw or “unprocessed” EEG monitoring as DSA in the measurement of depth of hypnosis.^{4,9}

We previously performed some observational studies to investigate the specific anaesthetic drug and age-dependent DSA signatures in children.^{1,10} A specific DSA pattern of general anaesthesia with sevoflurane in children aged 6 months to 12 years exists of the appearance of high delta and alpha power on the spectrogram.¹

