2. OBJECTIVES

Primary Objective: the influence of density spectral array monitoring with the Narcotrend™ monitor on the speed of emergence from general anaesthesia with sevoflurane. The speed of emergence is defined as the time interval between the end of hypnotic drug application and the moment when discharge criteria from the operating room are met (defined as a Steward score ≥ 3).

Secondary Objectives:

- Total time from discontinuation of anaesthetic drug delivery until discharge from the post anaesthesia care unit.
- The incidence of postoperative delirium by the Cornell Assessment of Postoperative Delirium (CAPD) score.^{14,15}
- The difference in intra-operative blood pressure between the intervention group and the control group.
- Differences of depth of hypnosis during the procedure, as measured by the Narcotrend monitor™.
- Incidence of recall of events during the procedure (awareness)
- Adverse events

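### Section 10.2 does not make the child the unit of the depth-of-hypnosis comparison, its three DSA categories do not divide up all patterns, and masked categorisation is not stated (minor)

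*Combined protocol and SAP*

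**What the plan says.** Section 2 lists the comparison as a secondary objective, "Differences of depth of hypnosis during the procedure, as measured by the Narcotrend" monitor, and section 8.1.2 repeats it as a secondary endpoint. Section 5 explains that control children are also attached to the monitor, with its screen covered, so that their EEG can be compared later with the intervention group's.

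Section 10.2 introduces the analysis with "Posthoc intergroup comparison of hypnotic depth as measured by DSA is performed as follows" and continues: "DSA patterns recorded during the procedure are categorised and assigned to three conditions of the specific DSA pattern for GA". The three conditions are:

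- the reference state, given as "appropriate DoH (presence of high power delta and alpha oscillations on the power spectrum";
- the state in which theta is added, given as "to deep DoH (presence of high power delta, alpha and theta oscillations on the power spectrum";
- light, defined as "presence of high power delta with the absence of high power alpha oscillations and the presence of high power beta oscillations".

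The test follows: "Intergroup comparison will be performed by a means of a chi-square test". Section 1.2 describes the sevoflurane pattern at these ages in the same terms as the first condition: it "exists of the appearance of high delta and alpha power on the spectrogram".

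On blinding, section 8.2 masks the investigator who assesses emergence and accepts that the person giving the anaesthetic cannot be masked. It does not mention whoever categorises the recordings.

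**The concern.** A chi-square test needs independent units, each in exactly one category. The wording secures neither.

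DSA is a display over time, so one child can show several patterns during a procedure. Section 10.2 counts patterns, and gives no epoch length, time point or per-child summary. Two analysts could build different tables from the same recordings, and a table of pooled patterns would overstate the evidence.

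The category definitions leave some patterns with two homes and others with none, and the readable text gives no threshold for high power. Whoever categorises must then choose, and the choice can differ by group if the group is known.

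At stake is the trial's own evidence on whether DSA guidance changed depth, which is the use that section 5 gives for the control group's EEG. The primary comparison of emergence times does not depend on it.

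**Working it through.** **1. Unit of analysis.** The plan gives no figure for this comparison, so there is none to reproduce. Inputs:

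- 51 children per arm, from section 4.4, where it is the sample size for the primary endpoint; used here only as an arm size.
- Three categories in two groups, so (2−1)(3−1) = 2 degrees of freedom and a 5% critical value of 5.991.
- Assumed, because the documents give none of these: m patterns per child of 5, 12 or 30; within-child correlation (ICC) of 0.05, 0.1 or 0.2; shares of 60/25/15% for appropriate/deep/light.

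Pooling multiplies the variance by the design effect DE = 1 + (m−1) × ICC. The upper tail of a chi-square with 2 degrees of freedom is exp(−x/2), so the null rejection rate is about exp(−5.991/(2 × DE)). For m = 12 and ICC = 0.1: DE = 1 + 11 × 0.1 = 2.1, and exp(−5.991/4.2) = 0.240.

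The simulated columns come from 3,000 null trials per setting (Dirichlet-multinomial).

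| m | ICC | DE | Pooled, formula | Pooled, simulated | One modal label per child, simulated |
|---|---|---|---|---|---|
| 5 | 0.05 | 1.20 | 0.082 | 0.078 | 0.049 |
| 5 | 0.1 | 1.40 | 0.118 | 0.120 | 0.051 |
| 5 | 0.2 | 1.80 | 0.189 | 0.180 | 0.051 |
| 12 | 0.05 | 1.55 | 0.145 | 0.138 | 0.045 |
| 12 | 0.1 | 2.10 | 0.240 | 0.241 | 0.043 |
| 12 | 0.2 | 3.20 | 0.392 | 0.388 | 0.050 |
| 30 | 0.05 | 2.45 | 0.294 | 0.294 | 0.033 |
| 30 | 0.1 | 3.90 | 0.464 | 0.472 | 0.047 |
| 30 | 0.2 | 6.80 | 0.644 | 0.636 | 0.047 |

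Pooling gives 8% to 64%. One label per child gives 3% to 5%.

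**2. Categories.** With each of delta, alpha, theta and beta either high or not, there are 2^4 = 16 combinations. The 8 without high delta fit no definition. The 8 with high delta sort as follows.

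| High bands besides delta | As worded | If theta decides between appropriate and deep |
|---|---|---|
| none | none | none |
| theta | none | none |
| beta | light | light |
| theta, beta | light | light |
| alpha | appropriate | appropriate |
| alpha, beta | appropriate | appropriate |
| alpha, theta | appropriate and deep | deep |
| alpha, theta, beta | appropriate and deep | deep |

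As worded, 4 fit one category, 2 fit two and 2 fit none. With theta as the discriminator, 6 fit one and 2 fit none. These are counts of definitions, not of how often the patterns occur.

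**3. Choice of per-child measure.** Suppose the shares are 60/30/10% in one group and 60/10/30% in the other: a shift from deep to light with the appropriate share unchanged. With 51 per arm, m of 5 to 30 and ICC of 0.05 to 0.2, a Mann-Whitney test on the per-child appropriate proportion rejected in 4% to 6% of simulated trials, about the null rate. Chi-square on one modal label per child rejected in 91% to 97%. The scenario is chosen to show the weakness, not to predict the data.

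In the null simulations of step 1, with a setting of one pattern per child added, testing all three proportions without correction gave at least one rejection in 11% to 13% of trials. One measure therefore has to be named in advance.

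**The case against.** - **Nobody wrote that patterns will be pooled.** The other chi-square in section 10.2, on delirium, naturally counts children, and on that reading the level holds. This stands: a reader might infer that the planned test has an inflated error rate, but the documents allow pooling without stating it.
- **Theta is the evident discriminator.** Sorting into three conditions implies one home per pattern, and the deep definition differs from the appropriate one only by theta. That is a fair reading and it removes the overlap. It is not written, though: the light definition spells out an absence (alpha), while the appropriate definition spells out none for theta, nor does section 1.2. The gaps remain on either reading.
- **The gaps may hardly matter.** No frequencies are given, and the unplaced patterns may be rare. This stands as a limit on the size of the problem.
- **Procedures may be specified elsewhere.** Section 8.3 refers to a flowchart that is not visible in the text available, so the unit or the masking might be shown there. Section 12.1 says that analysis uses coded numbers, but this protects identity, not allocation. A reader might infer that the recordings will be categorised with the group known; the documents say neither that nor the opposite.
- **The analysis is called post hoc.** That may mean exploratory, or only that categorising happens after the procedure. In either case the comparison belongs to a listed endpoint and has a planned test.

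**Conclusion.** The point holds as an under-specified secondary analysis. Section 10.2 neither makes the child the unit nor gives categories that place every pattern exactly once, and no readable section masks the categorisation.

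The error rate of about 8% to 64% applies only if patterns are pooled, and it rests on assumed numbers of patterns, correlations and category shares. It is not an estimate for this trial. The overlap depends on the literal wording; the gaps do not, but how often they arise is unknown. The absence of a stated unit and of masking is subject to the flowchart that could not be checked.

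The severity is minor. A reader might carry the doubt over to the emergence result, but the primary endpoint uses a different measurement, a masked assessor and a different test.

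**What to change.** In section 10.2:

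1. Make the child the unit of analysis, in one of three ways:
   - one label per child by a rule set beforehand (for example, the category that takes up most of the recorded time), keeping the planned chi-square;
   - per-child proportions of recorded time in each category, with one main measure named in advance that separates too deep from too light, for example time in *to deep*, and the rest descriptive. Time in *appropriate* is a poor choice because it can miss a shift from deep to light;
   - a model that treats the child as a cluster.
2. Reword the three definitions so that they are mutually exclusive. The band criteria are for the sponsor to set.
3. Add an unclassified category, and say beforehand how it enters the comparison.
4. Have the stored recordings categorised with the group label removed.
5. Say what post hoc means here.

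The cost is a few lines of text and slightly more analysis work on recordings that are collected anyway. No new data are needed, and the sample size and primary analysis do not change.

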10.3 Other study parameters

Descriptive statistics will be applied to demographic variables, continuous variables such as discharge times, incidence of recall of events during the procedure (awareness) and adverse events. All datasets will be tested for normality by means of the Shapiro-Wilk normality test.

10.4 Interim analysis (if applicable)

We will not perform an interim analysis.

11. ETHICAL CONSIDERATIONS

11.1 Regulation statement

The study will be conducted according to the principles of the Declaration of Helsinki (seventh revision 2013) and in accordance the Medical Research Involving Subjects act (WMO).

11.2 Recruitment and consent

According to the procedural steps described in the 2010 version of the CONSORT flow diagram (<http://www.consort-statement.org/consort-statement/>) patients will be assessed for eligibility to be enrolled in the study as soon as possible after the paediatric surgeon or urologist has made the decision to operate the patient. Preferably patients and/or their legal representatives will be provided with the patient information folder (PIF) during their visit at the pre-anaesthetic assessment clinic. Recruitment of subjects will be done by the clinical investigators ([name], [name], [name] and [name]). The Dutch PIF's and informed consent forms for both the parents and patients are attached as separate documents.

11.3 Objection by minors or incapacitated subjects (if applicable)

Minors cannot be forced to undergo interventions against his or her will. This study will be conducted according to the Code of Conduct applicable to minors as written by the Pediatric Association of the Netherlands (Nederlandse Vereniging voor Kindergeneeskunde). The parents will be informed about the possibility to withdraw their child at any moment in the study without consequences for the medical care in an information letter they will receive upon inclusion.

11.4 Benefits and risks assessment, group relatedness

Patients randomised to the intervention group might benefit from a better GA technique. Patients randomised to the control group, thus receiving standard treatment, can neither expect any benefit nor any disadvantages from participating in the study.

11.5 Compensation for injury

The sponsor/investigator has a liability insurance which is in accordance with article 7 of the WMO.

The sponsor (also) has an insurance which is in accordance with the legal requirements in the Netherlands (Article 7 WMO). This insurance provides cover for damage to research subjects through injury or death caused by the study.

The insurance applies to the damage that becomes apparent during the study or within 4 years after the end of the study.

11.6 Incentives (if applicable)

Not applicable

12. ADMINISTRATIVE ASPECTS, MONITORING AND PUBLICATION

12.1 Handling and storage of data and documents

All personal data will be coded by serial numbers. Only the project leader ([name]) will have access to the key. Statistics will be performed with the coded numbers. Published data from this study cannot be traced to a specific child. All coded data will be stored in a secure place for a minimum of 15 years. We will use Castor EDC as an electronic data capture. All personal data will be handled according to the EU General Data Protection Regulation and the Dutch Act on implementation of the General Data Protection Regulation.

12.2 Monitoring and Quality Assurance

The 'Monitoringplan' is constructed in accordance with the least ErasmusMC guidelines. The Clinical trial center will be contacted for the fulfilment of the 'Monitoringplan'.

12.3 Amendments

Amendments are changes made to the research after a favourable opinion by the accredited METC has been given. All amendments will be notified to the METC that gave a favourable opinion.

All substantial amendments will be notified to the METC and to the competent authority.

Non-substantial amendments will not be notified to the accredited METC and the competent authority, but will be recorded and filed by the sponsor.

12.4 Annual progress report

The sponsor/investigator will submit a summary of the progress of the trial to the accredited METC once a year. Information will be provided on the date of inclusion of the first subject, numbers of subjects included and numbers of subjects that have completed the trial, serious adverse events/ serious adverse reactions, other problems, and amendments.

12.5 Temporary halt and (prematurely) end of study report

The investigator/sponsor will notify the accredited METC of the end of the study within a period of 8 weeks. The end of the study is defined as the last patient's last visit.

The sponsor will notify the METC immediately of a temporary halt of the study, including the reason of such an action.

In case the study is ended prematurely, the sponsor will notify the accredited METC within 15 days, including the reasons for the premature termination.

Within one year after the end of the study, the investigator/sponsor will submit a final study report with the results of the study, including any publications/abstracts of the study, to the accredited METC.

12.6 Public disclosure and publication policy

The investigators are responsible for the public disclosure and publication of the research data. No sponsor is involved in the publication of the data.

Parents may request an overview of the study results after completion of the study.

13. STRUCTURED RISK ANALYSIS

13.1 Potential issues of concern

Not applicable (see chapter 13.2)

13.2 Synthesis

Only paediatric patients who are scheduled for a surgical or urological procedure requiring general anaesthesia supplemented with caudal analgesia, aged 6 months until 12 years, are eligible to be included in this study. Participants of this study will not be exposed to an increased risk compared to the (negligible) risk of GA.

The aim of this trial is to investigate if there is a significant benefit of DSA guided GA compared to GA guided by MAC and assessment of clinical signs of hypnotic depth. Based on our personal experience we expect that DSA guidance will result in a faster recovery. We do not expect any negative effects of DSA guidance of GA.

